There have been more than 900 papers published that measure patient-centred care or one of its components [14]. However, only two measurement instruments for attitudes towards patient-centredness in undergraduate medical students have been identified: the Doctor Orientation Scale and the Patient-Practitioner Orientation Scale (PPOS); of these two, the PPOS has been used much more extensively [15]. The PPOS was developed in 1999 to measure the attitudes of medical students towards patient-centredness [16]. It differentiates between patient-centred versus doctor-centred or disease-centred orientation, measuring attitudes along 2 dimensions: 'sharing' and 'caring' [17]. It has been used to assess attitude changes towards patient-centredness in medical student cohorts as they progress through the clinical curriculum.

The PPOS is available in 13 languages. It has been translated into German and the degree of medical students' patient-centeredness assessed in 2 student samples in Freiburg, Germany and in Basel, Switzerland [18]. Construct validity was tested using factor analysis. Based on factor analysis and tests of internal consistency, a shortened version with 6 items for each of the 2 subscales "sharing" and "caring" was generated (PPOS-D12). PPOS-D12 (see English-language version at Appendix 1) was found to be a reliable instrument to assess patient-centeredness among medical students in German-speaking countries.

In a longitudinal survey of medical students' attitudes toward patient-centred care in Greece, students' attitudes were significantly less patient-centred at the end of their studies compared to the beginning of their clinical curricula (mean score in year 4: 3.96; mean score in year 6: 3.81; $P < 0.001$) [17]. In a South African study, medical students from all undergraduate six years took the PPOS survey. There was a decrease in mean scores (from 2.65 in first-year students to 2.25 in final-year students), with the most pronounced decrease in the first two years of study [15]. [19]. In a year-long study of resident physicians at a university hospital in Tokyo, PPOS scores reduced significantly over the year (mean score at start of year: 4.5, SD 0.48; mean score at end of year: 4.39, SD 0.51; change: -0.11, SD 0.42) [20].

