We have only identified one study that assessed the effect of an intervention on students' levels of patient-centredness. In this uncontrolled UK study, first-year dental undergraduates were given an attitudinal questionnaire to complete before and after their behavioural science course. No significant difference was found between their mean pre- and post-course PPOS scores (pre-course mean scores: 3.44 SD 0.33; post-course mean score: 3.37, SD 0.19; $P > 0.05$). We have found no controlled trials that test the effect of interventions on medical students' levels of patient-centredness, and no trials that look at the effect of early patient contact in the form of an unaccompanied visit to a patient in their home.

Aim of the study

The aim of this study is to assess how a structured, in-depth, home-based interview with a patient with a chronic illness affects first-year medical students' patient-centredness.

A nested study will assess whether the GP's level of patient/doctor-centredness affects changes in their student's level over the year.

Methods

Study setting

The study will take place in the Berner Institut für Hausarztmedizin (BIHAM) at the University of Bern, Switzerland, and a subset of the >700 General Practitioner (GP) teaching practices that are affiliated to it.

Study participants

The population will be medical students who are in the first year of their studies (their first Bachelor year) at the University of Bern, during their longitudinal placements in primary care. The GP teachers are family doctors that are accredited by BIHAM to take medical students.

Study design

This will be a randomised controlled trial. During their first Bachelor year, each medical student will spend a series of six half-days at the practice of a GP teacher that she/he has been allocated to. Students will be randomly assigned to either the intervention or the sham comparator which will take place during their last half-day in their practices. All students will complete an on-line version of the PPOS-D12 questionnaire at the start of the academic year and once more after the last half-day at their GP teachers' practices.

Intervention

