At the end of their students' attachments, their GP teachers will complete a SurveyMonkey questionnaire that asks them to complete the PPOS D12 form. Consent to use these data for research will also be requested.

Each of these questionnaires will ask for the participant's name, so that pre-intervention, post-intervention, and GP's data can be linked and compared.

Outcome measures

The primary outcome measure will be the change in students' PPOS-D12 scores from baseline (at the start of the academic year) to the end of their year-long primary care attachment.

Secondary outcomes will be the effect of students' gender, previous experience and prior exposure to chronic illness in the participant or her/his close relatives and friends on their PPOS-D12 scores

A nested study will measure the strength of association between the GP teachers' own levels of patient/doctor-centredness and changes in their students' levels over the year.

Development of the intervention

Following a literature review and discussion, RF, [name] and MH developed a patient interview pro-forma which was designed to identify patients' views on their illnesses, how it affects their lives in physical, psychological and social terms, and how their relationships with their GPs impacts on their lives. The sections of the interview pro-forma map across to Mead and Bower's conceptual framework of patient-centredness given above [22].

Six medical students who had been visiting their GP teachers for eight half-days per year since their first year of study agreed to pilot the intervention in November 2017. The GP teachers were asked to select a patient with a chronic illness for their students, and to organise 2.5-hour interviews, half of the students at the patients' home and in the other half in the teaching practices. Students were asked to use the questionnaire pro-forma. In addition, the students each had a 30-minute interview with a practice nurse to assess their perceptions of the effect of the illnesses on their patients, and finally a one-hour discussion with their GP teacher to reflect on their encounters with the patients, discuss their findings, and talk about any difficulties that may have arisen.

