- Students. In a tailored informed consent procedure, students will be given a 'high-level description' of the study objectives with only superficial information on the study interventions, as accepted by ethics committees in similar studies. They will be informed that they are randomised to one of two study groups, without revealing that one is an intervention and the other is a sham comparator. The aim of this is to minimise performance and other reporting biases.
- GP teachers. A similar approach will be taken with information for the GP teachers, so that they also have only a 'high-level' description of the study objectives.

Statistical analysis

Descriptive statistics will be used to describe the relationships between student demographics and PPOS scores. Mean pre- and post-test PPOS scores will be compared using paired *t* tests. Differences between PPOS scores in the intervention and control groups will be examined with unpaired *t* tests. For the nested study, GPs' PPOS scores and changes in their students' PPOS scores will be compared using paired *t* tests.

The sample size calculation for the primary outcome was based on reported mean reduction of 0.11 in the PPOS score over one year in a group without any intervention [20], and a mean increase of 0.05 in the intervention group. We therefore assumed a mean difference 0.16, with a standard deviation of 0.42. The study was designed with a 5% level of significance and a 90% power to reject the null hypothesis of equivalence between the two groups. To achieve this objective, 220 students would be required (110 for each group). Assuming a 20% drop-out, we therefore aimed to enrol a total of 275 students.

Discussion

This research will consider the effect of an in-depth, structured interview with a patient with a chronic illness on changes in first-year medical students' levels of patient-centredness. There is existing evidence that medical students' levels of patient-centredness reduce over their student years, and this study will contribute to an understanding of how this reduction can be minimised or reversed.

Strengths

To our knowledge, this is the first randomised controlled trial that has been designed to study the effect of an intervention on medical students' levels of patient-centredness. The intervention materials were carefully developed and piloted by GP teachers and medical students, and therefore grounded in their clinical and educational experience.

Limitations

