Although the research team will give participants information about the study in a presentation and in correspondence, there is a risk that fewer students than anticipated consent to take part in the study. While the researchers aim to blind participants to the nature of the comparison, i.e. that one intervention is the intervention and the other is a sham comparator, control intervention, participants may guess the researchers' intentions, and this may result in bias in their responses. The power calculations have been based on data from other published studies, but these may not be directly comparable to our own study. Our control intervention has been chosen because of evidence that teaching dental students about communication skills does not affect their levels of patient-centredness, but it is possible that our communication skills intervention will indeed have an effect the levels of our medical students' patient-centredness, and thus not be a truly inactive control.

Expected impact

One of the aims of BIHAM's clerkships in primary care is to shift the medical students' focus towards 'professionalism', and patient-centredness is an important aspect of professionalism. This study will assess whether a single in-depth structured interview with a patient, followed by a de-briefing interview with the patient's GP, can contribute to achieving this aim.

Quality assurance

The study may be monitored or audited in accordance with the current approved protocol, relevant regulations and standard operating procedures.

Confidentiality

The research team will ensure that the participants' anonymity is maintained. As soon as each student's pre- and post-intervention questionnaires have been matched with each other and those of their GP teachers, each participant will be identified only by a participant ID number on all study documents and any electronic database. All documents will be stored securely and only accessible by study staff and authorised personnel. Under no circumstances will the identifiers be made available to individuals outside the research team.

Dissemination

Results will be published in peer-reviewed scientific journals as well as by conference presentations. The researchers will publicise the project findings within their university and the Swiss health system, for example in newsletters, websites, meetings and local journal publications.

Funding

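### The between-arm t test uses baseline PPOS-D12 only by subtraction; ANCOVA on the same linked data would generally be more precise (optional free improvement)

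*Combined protocol and SAP*

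**What the plan says.** All references are to the combined protocol and SAP.

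- **Outcome measures:** "The primary outcome measure will be the change in students' PPOS-D12 scores from baseline" to the end of the year-long attachment.
- **Statistical analysis:** "Differences between PPOS scores in the intervention and control groups will be examined with unpaired" t tests. Beyond descriptive statistics, the section plans only paired and unpaired t tests. No regression, ANCOVA or baseline covariate appears anywhere in the document.
- **Study design:** "All students will complete an on-line version of the PPOS-D12 questionnaire at the start of the academic year", and again after the last practice half-day.
- **Data collection:** questionnaires carry names "so that pre-intervention, post-intervention, and GP's data can be linked and compared".
- **Sample size (in Statistical analysis):** "We therefore assumed a mean difference 0.16, with a standard deviation of 0.42". The 0.42 is the SD of change in the resident cohort described in the Background: "mean score at start of year: 4.5, SD 0.48; mean score at end of year: 4.39, SD 0.51; change: -0.11, SD 0.42".

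The sentence on the unpaired test does not say which score is tested. The Abstract says that changes will be calculated and the groups' mean scores compared. The primary outcome definition and the SD used for sample size both point to change scores, and that is the reading taken here.

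**The concern.** A t test on change subtracts the whole of each student's baseline score. That is the most precise use of baseline only if end score rises one-for-one with baseline. When the true slope is below 1, as measurement error and regression to the mean usually make it, full subtraction carries surplus baseline noise into the outcome. ANCOVA estimates the slope and removes that noise. Under randomisation it targets the same difference between arms.

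What is at stake is precision: the width of the confidence interval and the power obtained from a fixed number of students. Bias and type I error are not at stake. The loss deserves attention because the stated inputs give about 80% power at 220 students rather than the stated 90% (a separate matter), and because the Limitations section accepts that fewer students than anticipated may consent.

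**Working it through.** **Inputs.** Difference 0.16, change SD 0.42, 110 per arm and 5% significance come from Statistical analysis. Sidedness is not stated; two-sided is assumed. The start SD of 0.48, end SD of 0.51 and change SD of 0.42 come from the resident cohort in the Background. That these SDs apply to first-year students completing PPOS-D12 is an assumption.

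**The plan's own figure.** n per arm = 2 × [0.42 × (1.960 + 1.282) / 0.16]² = 144.8, so 145 (146 by the noncentral t) for 90% power. The plan's 110 per arm corresponds to 80% power (109 by the normal approximation, 110 by the t). Power for the change-score test at 110 per arm is 80.3%, and that is the baseline for the comparison below.

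**Implied correlation and slope.**
- r = (0.48² + 0.51² − 0.42²) / (2 × 0.48 × 0.51) = 0.3141 / 0.4896 = 0.64.
- Slope = r × 0.51 / 0.48 = 0.68.

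**Splitting the change variance.**
- Residual variance given baseline: 0.51² × (1 − r²) = 0.1530, so the ANCOVA residual SD is 0.391.
- Surplus from fixing the slope at 1: (1 − 0.682)² × 0.48² = 0.0234.
- Sum: 0.1530 + 0.0234 = 0.1764 = 0.42².
- Variance ratio, ANCOVA to change: 0.1530 / 0.1764 = 0.868, a reduction of 13%.

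**Power and precision** (noncentral t, difference 0.16; half-width = t × SD × √(2/n)):

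| Analysis | SD | Power, 110 per arm | Half-width, 110 per arm | n per arm for 90% |
|---|---|---|---|---|
| t test on change | 0.42 | 80.3% | 0.112 | 146 |
| ANCOVA | 0.391 | 85.5% | 0.104 | 127 |

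At 146 per arm, power would go from 90.0% to 93.6%. In a simulation of 20,000 trials at 110 per arm with these SDs, both methods had a mean estimate of 0.160. Power was 0.802 for change and 0.852 for ANCOVA, and type I error 0.051 and 0.048.

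**Sensitivity.** Moving each of the three SDs by its rounding error (±0.005) puts r at 0.63 to 0.66 and the gain at 4 to 6 points. The documents give no correlation for these students, so r is varied at 110 per arm:

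| Held fixed | r | Change: power (half-width) | ANCOVA: power (half-width) |
|---|---|---|---|
| Change SD 0.42, equal start and end SDs | 0.5 | 80.3% (0.112) | 90.1% (0.097) |
| Same | 0.8 | 80.3% (0.112) | 84.3% (0.106) |
| SDs 0.48 and 0.51 | 0.5 | 66.4% (0.132) | 76.3% (0.117) |
| Same | 0.8 | 96.4% (0.084) | 97.1% (0.081) |

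With SDs of 0.48 and 0.51 the slope reaches 1 at r = 0.48 / 0.51 = 0.94. There the two methods have the same residual SD and ANCOVA gains nothing.

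**If end scores are meant.** The SD is 0.51 and power at 110 per arm is about 64%. Moving to ANCOVA would then gain about 21 points (64.3% to 85.8% by the normal approximation), with variance 41% lower: 1 − 0.1530 / 0.2601.

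**The case against.** The strongest case for leaving the plan alone is that an unpaired t test on change matches the declared primary outcome, is valid and unbiased, and already uses baseline. All of that stands. A reader might infer that baseline is ignored. On the change-score reading it is not: it is subtracted, and what is missing is an estimated slope.

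The gain is also modest and its size is borrowed. A saving of 0.008 in half-width is small on a six-point response scale, and the correlation comes from resident physicians. The Limitations section itself warns: "The power calculations have been based on data from other published studies, but these may not be directly comparable to our own study". This stands too, so the gain is given as a range that runs down to nothing as the slope nears 1.

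Two further inferences should be resisted. One is that ANCOVA repairs the sample size, or conversely that it never could at 110 per arm. It falls short at 85.5% under the resident SDs, but reaches 90.1% at r = 0.5 with change SD 0.42. The other is that the dental-student SDs in the Background ("pre-course mean scores: 3.44 SD 0.33; post-course mean score: 3.37, SD 0.19") show a much larger benefit. That study was an uncontrolled course, and the documents give neither its change SD nor its correlation, so nothing is built on it here.

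Finally, stating which score is tested may matter more than choosing ANCOVA over change. Under the resident SDs, end score against change is about 64% against 80%, a larger step than 80% to 86%. That is right, and the fix settles both.

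**Conclusion.** The point holds as an optional improvement in efficiency; the planned test is not an error. Under the resident-cohort SDs, ANCOVA gains about 5 points of power (80.3% to 85.5%) and narrows the interval by about 7% (0.112 to 0.104), without reaching the stated 90% at 110 per arm. Its direction held in every scenario tried with a slope below 1; its size, about 1 to 10 points for r from 0.5 to 0.8, depends on a correlation that the documents do not give for these students. The figures assume a two-sided test and 110 analysed students per arm. They take the test to be on change scores; if it is on end scores, the loss is much larger. The mismatch between 90% power and 220 students is a separate and weightier matter.

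**What to change.** Before outcome data are analysed, specify the primary analysis as a linear regression of end-of-year PPOS-D12 on randomised arm with baseline PPOS-D12 as covariate. Report the adjusted mean difference with its 95% CI. If a t test is kept, state that it compares change scores.

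The cost is a change of wording and one degree of freedom. No extra students or questionnaires are needed, because a change score already requires the linked baseline.

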Appendix 1. PPOS-D12 English translation

Possible Likert-scale responses: 'I completely agree'; 'I agree'; 'I agree slightly'; 'I disagree slightly'; 'I disagree'; 'I completely disagree'.

1. Although treating patients today is not so personal anymore, it is ultimately a small price for medical advancement.
2. The most important part of the normal visit is the physical examination.
3. Patients should rely on the knowledge of their doctors and not try to inform themselves about their condition.
4. When doctors ask a lot of questions about a patient's personal situation, they are too involved in private matters.
5. When doctors are really good at diagnosis and therapy, their treatment of patients is not so important.
6. Many patients keep asking questions without really learning anything new.
7. Patients tend to want to hear that everything is good, rather than real information about their health.
8. When doctors first try to be open and make a warm-hearted impression, they will not be so terribly successful.
9. If patients disagree with their doctors, it shows that they disrespect their doctors and do not trust them.
10. The patient must always be aware that the doctor is responsible.
11. It is not so important to know the cultural background of a patient and his life situation in order to treat his illness.
12. When patients get their own medical information, it often confuses them more than it helps them.

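### The nested study's paired t test compares a GP score level with a student change score, so it will be significant whatever the association and cannot measure it

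*Combined protocol and SAP*

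**What the plan says.** Under Outcome measures, the nested study is to "measure the strength of association between the GP teachers' own levels of patient/doctor-centredness and changes in their students' levels over the year". The Abstract gives the same objective. Aim of the study puts it as an effect: "A nested study will assess whether the GP's level of patient/doctor-centredness affects changes in their student's level over the year".

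The two variables are defined under Data collection and Outcome measures. At the end of the attachment, "their GP teachers will complete a SurveyMonkey questionnaire that asks them to complete the PPOS D12 form", so each GP contributes one score at one time, which is a level. The student variable is the difference between two PPOS-D12 scores, one from the start of the academic year and one from the end of the attachment. Appendix 1 lists six ordered response categories without their numeric coding.

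The Statistical analysis section has one sentence on the nested study: "For the nested study, GPs' PPOS scores and changes in their students' PPOS scores will be compared using paired" *t* tests. No correlation, regression or other measure of association appears anywhere in the document. The sentence on descriptive statistics covers student demographics only.

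**The concern.** A paired t test has the null hypothesis that the mean of (GP score minus student change) is zero. It suits two measurements of the same quantity. Here one member of the pair is a level and the other is a difference centred near zero, so equality of their means is not a hypothesis anyone holds. The mean of the paired difference also does not depend on the correlation between the two variables, and that correlation is what the objective asks about.

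Followed as written, the nested study would return an extremely small p-value whether GP attitude is positively, negatively or not at all related to student change. Its question would stay unanswered, and a careless reader could take the p-value as evidence that GP attitude matters.

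**Working it through.** **The plan's own figure.** None is given for the nested study. The only sample size, 220 students, is for the primary outcome, and it serves here only as the largest plausible number of pairs after drop-out. It does not reproduce as stated: a difference of 0.16, SD 0.42, two-sided 5% and 90% power need 145 per arm (290 in total), while 110 per arm gives about 80% power. That is a separate matter and nothing below depends on it.

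**Inputs**

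- Student change: Statistical analysis assumes a "reported mean reduction of 0.11 in the PPOS score over one year in a group without any intervention" and "a mean increase of 0.05 in the intervention group". With 1:1 allocation the overall mean is (-0.11 + 0.05)/2 = -0.03. The SD is 0.42.
- GP level: not given, so this is an assumption. The resident-physician study cited in Background reports an end-of-year mean of 4.39 (SD 0.51). Because those are not Swiss GPs answering the PPOS-D12, the check is repeated at 2.25, the lowest mean cited in Background, and at 1.0, below any mean cited.
- True correlation r between GP score and student change: varied.

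**Formula**

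SD of the paired difference = sqrt(0.51² + 0.42² - 2 × r × 0.51 × 0.42)

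t = (GP mean - mean change) / (SD of difference / sqrt(n))

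At GP mean 4.39, r = 0 and n = 220:

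- SD of difference = sqrt(0.2601 + 0.1764) = 0.661
- Standard error = 0.661 / sqrt(220) = 0.0445
- t = (4.39 + 0.03) / 0.0445 ≈ 99

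The same study's start-of-year values (4.5, SD 0.48) give t = 4.53 / sqrt((0.48² + 0.42²)/220) = 105.3.

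**Paired t over the range, 220 pairs**

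| GP mean | r = -0.5 | r = 0 | r = 0.5 |
|---|---|---|---|
| 4.39 | 81.3 | 99.2 | 139.0 |
| 2.25 | 41.9 | 51.2 | 71.7 |
| 1.0 | 18.9 | 23.1 | 32.4 |

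The largest p-value in the table is about 5 × 10⁻⁴⁸. t moves with r, but only through the SD of the difference. The decision never changes, and t cannot be read as a strength of association.

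**How close the means must be for a non-significant result.** At 220 pairs, the GP mean must lie within (critical t) × (SD of difference) / sqrt(220) of the mean student change. That is 0.03 points at r = 0.9, 0.09 at r = 0 and 0.12 at r = -0.9. The mean PPOS levels cited in Background run from 2.25 to 4.5.

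**Simulation** (4,000 data sets per scenario, bivariate normal, GP mean 4.39, 220 pairs)

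| True r | Paired t rejects | Correlation test rejects |
|---|---|---|
| 0 | 100% | 5.2% |
| 0.2 | 100% | 85.6% |
| 0.5 | 100% | 100% |
| -0.5 | 100% | 100% |

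With GP means of 2.25 and 1.0 the paired t test also rejected in every data set at 220 pairs. At 20 pairs it rejected in at least 99.97% of data sets in every scenario.

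**What a proper analysis could detect.** By the Fisher z approximation, tanh((1.96 + z for power)/sqrt(n - 3)), the detectable |r| is:

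- 220 independent pairs: 0.19 at 80% power and 0.22 at 90%.
- 110 independent pairs: 0.26 at 80% power and 0.30 at 90%.

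**The case against.** The core error is not defended: the test and both variables are named, and no other text supplies an association measure. The case on the other side is about weight and wording.

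- **It is only a nested objective, and probably a drafting slip.** The objective is worded consistently in three places, and one sentence names the wrong test. Randomisation, data collection and the primary comparison are untouched, and linkage of student and GP questionnaires is already planned. This stands as a limit on how far the point reaches. It does not rescue the sentence, which is the objective's only planned analysis.
- **Certain rejection is a practical matter, not a mathematical one.** The numeric coding is not stated, so a GP mean close to zero is not strictly excluded. This is correct, but such a mean would be far from every level the protocol cites.
- **A misleading positive reading is speculative.** A t near 100 with a mean difference above 4 points might itself alert the analyst. That is fair. The nested question would still have no answer.
- **The GP mean is borrowed from resident physicians.** True, which is why a range is shown. The conclusion holds throughout it.
- **220 pairs is a best case.** It needs every retained student's GP to respond and consent, and one student per GP. Neither is stated. For a true r of 0.3, a correlation test has over 99% power at 220 pairs, about 89% at 110 and about 57% at 50. This qualifies how informative the corrected analysis will be, not the need for it.
- **Adjusting for baseline and arm goes beyond the error.** A simple correlation or slope of change on GP score would repair it. The adjusted model is a recommended form, not the only valid one.

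**Conclusion.** The concern holds. The specified test cannot measure association. It will be significant with practical certainty under zero, positive or negative association, for any GP mean from 1.0 to 4.5 and with 20 pairs as well as 220. The exact t values rest on assumed GP means and SDs and on independent pairs. The conclusion needs only that GP scores lie well away from the near-zero mean student change. The sentence must be corrected before the nested study is analysed. The primary comparison of the two arms does not depend on it.

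**What to change.** In Statistical analysis, replace the sentence on the nested study with:

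- **Model.** A linear regression of the student's end-of-year PPOS-D12 score on the GP's PPOS-D12 score, with the student's baseline score and randomised arm as covariates. Report the GP slope with its 95% CI. Because baseline is in the model, the GP slope is the same whether the outcome is the end-of-year score or the change (change = end-of-year score - baseline), so the model still answers the stated question about change.
- **Strength of association.** The correlation between GP score and student change, with its 95% CI.
- **Clustering.** State whether a GP can have more than one student. If so, use standard errors clustered by GP.
- **Precision.** State the expected number of linked student-GP pairs and the association that number can detect, since the existing sample size covers the primary outcome only.

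The cost is a few lines of protocol wording. The questionnaires and their linkage are already planned, so no further data or participants are needed.

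### The sample size and the stated 90% power do not agree: 110 students per group gives about 80% power (two-sided 5%) on the protocol's own inputs

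*Combined protocol and SAP*

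**What the plan says.** The sample size paragraph is in Methods, under Statistical analysis. It expects a fall of 0.11 in the PPOS score without intervention and a rise of 0.05 with it, and continues: "We therefore assumed a mean difference 0.16, with a standard deviation of 0.42". The design target is "a 5% level of significance and a 90% power to reject the null hypothesis of equivalence between the two groups". The result is given as "To achieve this objective, 220 students would be required (110 for each group"), raised to 275 enrolled for 20% drop-out.

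The fall of 0.11 and the SD come from the study of resident physicians summarised in the Background, which reports "change: -0.11, SD 0.42". The planned comparison of the arms is in the same section: "Differences between PPOS scores in the intervention and control groups will be examined with unpaired" *t* tests. The section names no covariate adjustment and does not say whether the test is one- or two-sided.

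**The concern.** The difference, SD, significance level, power and group size are all given, so the calculation can be repeated. The standardised difference is 0.16/0.42 = 0.38, and 110 per group looks too few for 90% power at that size.

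This paragraph is the only justification for the size of the trial, and it concerns the primary outcome. If the power is overstated, a non-significant result will appear to come from a trial with a 1-in-10 chance of missing the target difference when the real chance is about 1 in 5. The Limitations section warns that fewer students than expected may consent. A stated 90% suggests a margin against that shortfall which does not exist.

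**Working it through.** **Inputs**

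- Difference in mean change: d = 0.11 + 0.05 = 0.16 (Statistical analysis).
- SD of the change: s = 0.42 (Statistical analysis, matching the cited study in the Background). It is the SD of a change score and the primary outcome is a change score, so the input is of the right kind.
- Significance level 5%, stated power 90%, two equal groups of 110, unpaired t test (Statistical analysis).
- Sidedness: not stated. I take two-sided as the main reading, because the null hypothesis has no direction, and check one-sided as well.

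**Trying to reproduce 110 per group**

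Normal approximation: n per group = 2 × (z_alpha + z_power)² × (s/d)², with (0.42/0.16)² = 6.8906. The t-based column solves the noncentral t power equation.

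| Test | Power | Calculation (normal) | n per group, normal | n per group, t |
|---|---|---|---|---|
| Two-sided 5% | 90% | 2 × (1.960 + 1.282)² × 6.8906 | 144.8, so 145 | 145.8, so 146 |
| Two-sided 5% | 80% | 2 × (1.960 + 0.842)² × 6.8906 | 108.2, so 109 | 109.1, so 110 |
| One-sided 5% | 90% | 2 × (1.645 + 1.282)² × 6.8906 | 118.0, so 119 | 118.7, so 119 |

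Of these, only the two-sided t test at 80% power gives 110.

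**Power at 110 per group**

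- Standard error of the difference = 0.42 × √(2/110) = 0.0566.
- Expected standardised difference = 0.16/0.0566 = 2.825.
- Two-sided power, normal: Φ(2.825 − 1.960) = 80.7%. Noncentral t with 218 degrees of freedom: 80.3%.
- Type II error = 100% − 80.3% = 19.7%, against 10% implied; the ratio is 1.97.
- One-sided 5% power: 88.1% (normal) or 87.9% (t).

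**Other explanations tested**

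- *Drop-out.* 220/(1 − 0.20) = 275 is right, so the discrepancy does not arise there.
- *All 275 analysed.* With 137.5 per group, two-sided power is 88.3% (t), still under 90%. This sets aside the protocol's own drop-out and is only an upper bound.
- *Rounded inputs.* For 110 per group to give 90% two-sided power (t), the difference would have to be about 0.184 or the SD about 0.364. Neither rounds to the stated 0.16 or 0.42.

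**What 90% would need**

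2 × 146 = 292 analysable students; 292/0.8 = 365 enrolled. On the normal approximation, 2 × 145 = 290 analysable and 290/0.8 = 362.5, so 363 enrolled.

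**The case against.** The strongest reply is that sidedness is not stated, so 80% rests on an inference. That is true and should be said. Under a one-sided 5% test the power is 87.9% and the type II error about 12%, so the overstatement would be much smaller; with all 275 analysed, one-sided power would exceed 90% (about 93%). But the one-sided reading does not reproduce 110, does not reach 90% with 220 students, and is stated nowhere, whereas the two-sided t test at 80% power gives exactly 110.

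A second reply is that the documents show an inconsistency, not which figure is the mistake. The team may have calculated for 80% and written 90%, or may have wanted 90% and miscalculated the number. The exact match suggests the first but does not prove it. This bears on the choice of remedy, not on whether the two figures conflict.

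Third, the Limitations section concedes that the published data behind the power calculation may not carry over to this study. That caveat concerns the inputs; it does not cover a wrong result from those inputs.

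Finally, misstated power does not bias the estimate, the confidence interval or the type I error, and 80% is a conventional level. This is correct: the harm is confined to planning and to the reading of a null result.

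**Conclusion.** The concern holds. With a difference of 0.16, an SD of 0.42 and a two-sided 5% unpaired t test, 220 analysable students give 80.3% power, not 90%. The plan is short by 36 students per group (146 − 110), or 72 in total, for the power it states. The conclusion assumes a two-sided test and takes the protocol's difference and SD at face value. On the one-sided reading the gap narrows to about 2 percentage points of power and 9 students per group (119 − 110), but the stated figures still do not agree.

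**What to change.** In the sample size paragraph, replace 90% power with 80% power and state that the 5% test is two-sided. The difference of 0.16, the SD of 0.42, 110 per group, 220 analysable and 275 enrolled can all stay. The cost is one sentence and a less favourable stated power; enrolment and conduct do not change.

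If the investigators did intend 90%, the number has to change instead: about 292 analysable students, or 365 enrolled at 20% drop-out, which is 90 more than planned (365 − 275). The choice is theirs, but the power and the sample size must be made to agree.
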